### 5.4 Inclusion/Exclusion Criteria

- *Describe the criteria that determine who will be included in or excluded from the study.*

**Participant Inclusion criteria:** We will focus our intervention in the geographic area directly surrounding the VA Puget Sound (Seattle and ALVA clinics) that has a high prevalence of poorly controlled hypertension. As part of project planning, we have worked with the Office of Analytics and Business Intelligence to utilize Geographic Information Systems (GIS) to identify and target high risk areas. This type of patient mapping is available nationwide, so this mechanism to identify and recruit participants is potentially generalizable. Specific maps are shown in Appendix 1 of attached IIR.

We developed our inclusion criteria to identify Veterans who will benefit the most, by focusing on Veterans up to age 75 (no age restrictions below age 75) with poorly controlled risks that are amenable to change. Specific inclusion criteria include poorly controlled hypertension (mean systolic BP > 150/90 mmHg) and one or more of the following CVD risks: overweight or obese (Body Mass Index (BMI)  $\geq 25 \text{ kg/m}^2$ ), current tobacco use, or a diagnosis of hyperlipidemia. Although we are selecting common conditions that increase cardiovascular risk, we are not excluding Veterans with other prevalent conditions (e.g. diabetes, arthritis, renal disease, or COPD), whose presence will be noted in the enrollment visit. We chose to focus on Veterans with elevations in systolic hypertension above the stage 1 level of 140 mmHg, given recent data regarding treatment of mild hypertension.

**Exclusion criteria:** We will exclude those who have been hospitalized 3 months prior to enrollment for a CVD admission (IHD, CVA or PVD), as these Veterans may be too ill to participate in this intervention. We will exclude patients with dementia or severe cognitive impairment that would not allow them to participate in the program; patients with a suicidal ideation and/or disruptive behavior flag in CPRS; patients with end stage renal disease on dialysis, given the unique care needs of this population; patients who have received palliative care or are enrolled in hospice care, given their limited life expectancy; Veterans enrolled in Home Based Primary Care, an all-inclusive home visit nurse program or those who live in care facilities (nursing homes, assisted living facilities); homeless Veterans and women who are pregnant or planning to become pregnant.

## 5.5 Study Evaluations

- Describe all evaluations to be conducted (including screening; tests/questionnaires that will be administered; any procedures that subjects will be required to complete) and data collection methods.

Include materials as an appendix or separate attachment. Only refer to attachments as A, B, etc. Do not refer to version #'s or dates of versions. During the course of the study, changes in the attachments will require IRB approval; however, those changes may not require a revised protocol.

The sources of data for this project will be participant interviews and medical records. The participant interviews will be collected specifically for this project while the medical record data will be obtained from existing sources. In order to evaluate the effectiveness of the proposed intervention, the study will administer baseline and exit interviews, conduct limited physical examinations where blood pressure, height and weight are measured, and, if needed, we will request the primary care provider order a blood test for potential participants. The proposed interview and limited physical exam will be administered at baseline and after the intervention period and will be conducted by study coordinators or research assistant. Only the study personnel will have access to any personally identifiable health information.

## **Measures**

### **Specific Aim 1**

Table 4 lists the health outcome measures. We will collect these outcome variables at baseline prior to randomization and at 12 months in both the intervention and control groups. Process and outcome data will be collected via the following sources: Patient Surveys: Baseline and 12-month surveys will be conducted by trained research staff. The administrative assistant and project manager will review all questionnaires and other data collection records, correct errors, and enter them into a password-protected database within 10 days of collection. Semi-structured Interviews: These will be conducted with purposive samples of Veterans upon exit from the program and at one year. Primary care staff will be interviewed after completing the intervention phase. Time Logs: Logs will be used to track time spent by the peer health coaches in intervention, attempting to reach patients, and key information about the content of those interactions. Administrative and Clinical Data Systems: These will be used to track patients' use of other VA inpatient and outpatient services.

### **Primary and secondary outcomes**

The primary outcome measures will be systolic blood pressure. At the baseline visit and the final 12 month exit call, the study staff will ask the participant to measure blood pressure three times. At the time of scheduling, study staff will ask if the participant has a blood pressure monitor and/or scale in their possession. If the participant does not have a monitor or scale, staff will mail them one from the VA office. The mean value for these readings will be used for the baseline and exit measurements, respectively.

Secondary outcomes will include Framingham Risk Score (FRS), individual CVD risks (BMI, LDL-c, tobacco use), health care utilization and health-related quality of life. A 10-year risk of total CVD (including myocardial infarction, angina, coronary revascularization, stroke, congestive heart failure and peripheral arterial disease) will be determined according to FRS algorithms, which include age, total and high-density lipoprotein-cholesterol, systolic blood pressure, treatment for hypertension, diabetes, and cigarette smoking. Individual components of this risk score are targets of the intervention (hypertension, hyperlipidemia, and smoking). The FRS algorithm has good predictive validity for CHD events (c statistics 0.74 and 0.77 for men

and women, respectively). Health care utilization will include outpatient visits, emergency department visits, and hospitalizations. Health care utilization will be obtained from VA administrative data and by participant self-report to capture non-VA health care utilization. Health-related quality of life will be measured by the Medical Outcomes Study 12-item measure, the SF-12. Two composite scales will be used to measure physical health (the physical component summary) and mental health (mental health component summary).

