### Study design overview:

We propose a randomized controlled trial to evaluate the effectiveness of **Vet-COACH**, a peer health coach program to control hypertension and reduce CVD risk among Veterans. The original program incorporated home visits by peer health coaches to deliver health education, counseling and goal setting support. Due to safety concerns and social distancing restrictions stemming from the COVID 19 pandemic, the program has transitioned to conducting all health coaching encounters, as well as enrollment and exit visits, via phone. This transition was implemented under IRB approval of the miscellaneous memo submitted at the beginning of the pandemic. These changes to conduct all health coaching encounters and exit surveys over the phone will be permanent for the remainder of the study. Our operations partners from NCP have developed extensive patient educational materials that will be used for the current study. We will train the peer health coaches to provide brief educational messages and link Veterans to existing clinical services at VHA, including their primary care PACT teams and community based programs. The main outcome will be a reduction in systolic blood pressure. Secondary outcomes are cardiovascular risk, as measured by the Framingham Risk Score (FRS), health care utilization and intermediate behavioral outcomes including patient activation, social support and health behaviors (e.g. diet and physical activity, medication adherence). *We will randomize a total of 200 individuals to the intervention group and 200 individuals to the control group.*

Our study design has limitations. Because of the nature of the intervention, we are unable to blind treatment assignment. The PI and [name] will provide overall supervision to the peer coaches. This model is necessary for program development. Because the intervention is being conducted at two sites, we are not proposing an economic evaluation to estimate cost-effectiveness, in part because such data would be of limited generalizability. Positive findings will lead to a larger multi-site trial that would include a cost-effectiveness analysis. These limitations are more than balanced by the strengths of this proposal. The proposed project is a prospective, randomized controlled trial that examines important outcomes with statistical power to detect clinically meaningful differences.

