### Description of Vet-COACH – a call-based peer health coach intervention:

The three goals of the peer health coach intervention include: (1) delivering brief health messages based on materials from the HPDP program, (2) acting as a community-clinic liaison and (3) providing expertise on the availability of community based resources for healthy lifestyle choices (e.g. places for physical activity, walking groups, grocery store tours, etc.) **The focus of the intervention will be the provision of brief health messages, goal setting and action planning around health behavior changes shown to decrease CVD risk** (e.g. healthy diet, regular moderate-intensity physical activity, tobacco cessation if applicable). Peer health coach education modules, examples of key messages and measures used to assess participant progress are outlined in Table 2. Required education modules for hypertension include: physical activity, nutrition, and medication adherence (and weight management if overweight or obese).

**Table 2. Veteran Peer Health Coach Required Education Module Topics, Examples of Goals and Key Messages, Referrals to Community or VHA resources, and Measures Used to Assess Intermediate Outcomes**

Behavioral targets	Goals and Key Messages	Referral to appropriate community or VHA resources	Intermediate outcome measures
Required modules – applies to all Veterans with Hypertension			
Blood Pressure	What is high Blood Pressure? Understand systolic & diastolic measurements. Tips to manage blood pressure.	Offer blood pressure cuff if subject does not have one. Record blood pressure measurements & report to PI, study nurse and/or PCP as needed.	Standard protocols
Physical activity	Avoid inactivity. Every 10 minute session of physical activity counts. Goal of moderate exercise for at least 30 minutes per day.	List of local physical activity resources provided to all participants Offer pedometers	IPAQ 
Nutrition	Healthy plate concept. Areas of focus will include reducing portion size, reducing fast food intake, avoiding processed foods high in sodium and carbohydrates, reduction of salt intake, increase in fruit and vegetable intake and decrease in total and saturated fat.	Encourage referral to VHA nutrition Offer healthy plate Grocery store tour Information on local resources (e.g., food banks, farmers markets)	Self-reported nutrition behavior  and food frequency (FFQ) 

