
**b) Randomization**

Following baseline assessments, a computerized randomization procedure will assign individuals to either the peer health coach intervention or to the usual care + education control group. Randomization of participants will occur in the order of completed enrollment visits. Randomization lists will be constructed in advance by the study biostatistician using variable

length blocks to ensure the groups are not unbalanced at any time. Concealment will be used to prevent the study staff from obtaining information on the sequence of assignment.

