**c) Usual care + education control arm**

Usual care consists of enrollment in the Primary Care Clinic or Women's Clinic at VA Puget Sound, plus an educational pamphlet with study materials provided at the baseline visit. The educational pamphlet will deliver the same information content as the intervention and consist of existing NCP materials (See Appendix 2 of attached IIR). We chose *not* to develop an attention control arm. Part of the process of the peer health coach intervention is the increased social support of the home visits. By providing "attention" in another way, we would not be able to test the effect of the increase in social support provided to intervention participants. Social support (or "attention") has been shown to be a powerful resource to maintain both physical and mental quality of life, despite the impacts of multiple chronic conditions. Perceived social support has been significantly related to health-related quality of life.

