
At follow up calls, the peer health coach will learn about patient challenges and concerns, review progress on implementing the self-management plan, provide targeted education to help with plan

implementation, revise self-management goals and the plan as the participant progresses, and make referrals to VHA and community resources. If deviations in medication adherence are noted, pillboxes will be offered. Blood pressure cuffs will be offered for home monitoring, as supported by a recent review of home blood pressure monitoring reporting moderate strength evidence. Participants will receive assistance with health system navigation.

If an intervention participant moves out of the Puget Sound area and does not have an assigned VA provider, health coaching encounters will be discontinued because the PI would not be able to notify the provider of possible medical issues that may arise during the encounters. If a participant moves out of the area and retains a VA provider (at either the VA Puget Sound or a VA in another state), we would continue to complete health coaching encounters and the PI will report medical concerns to their assigned VA provider listed in CPRS. Study staff will continue to complete the exit phone visit with participants regardless of continuation of health coaching visits.

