### Specific Aim 3: Determine intervention costs

These costs will include all labor and materials (pamphlets, home BP monitors, etc.) used in the intervention. We will administer weekly time sheets for all study personnel to estimate the amount of time they spend in various activities, and attribute the cost of these activities to either intervention costs or trial-specific costs, which are excluded from the intervention cost.

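### Phone-enrolled controls who own no blood-pressure monitor are sent one before randomisation, so the stated comparator of usual care plus education is wrong for them

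*Protocol*

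**What the plan says.** **Supply.** Protocol 5.5, Primary and secondary outcomes: "At the baseline visit and the final 12 month exit call, the study staff will ask the participant to measure blood pressure three times". Staff ask about a monitor and a scale when they schedule, and "If the participant does not have a monitor or scale, staff will mail them one from the VA office". The rule names no arm, and no loan or return is described.

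**Timing.** Protocol 5.1, Study design overview: "the program has transitioned to conducting all health coaching encounters, as well as enrollment and exit visits, via phone". Protocol 5.1 b): "Following baseline assessments, a computerized randomization procedure will assign individuals".

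**Monitor as intervention.** Table 2 in Protocol 5.1, in a required module: "Offer blood pressure cuff if subject does not have one". Protocol 5.1, Visit content: "Blood pressure cuffs will be offered for home monitoring, as supported by a recent review of home blood pressure monitoring reporting moderate strength evidence". Protocol 5.5, Specific Aim 3, counts "all labor and materials (pamphlets, home BP monitors, etc.) used in the intervention", and Protocol 5.6 and the SAP's Cost of intervention paragraph do the same. Protocol 5.2 also lists a scale among the items in the bag given to the intervention group.

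**Comparator.** Protocol 5.1 c) defines control as enrolment in the clinic "plus an educational pamphlet with study materials provided at the baseline visit". The SAP's primary hypothesis (section 6) is stated against usual care plus education. Neither mentions a monitor or scale.

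**SAP measurement text.** SAP section 5 has baseline pressure taken by a trained research assistant on a named device. It does not describe self-measurement or mailed monitors.

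**The concern.** The plan uses one device in two roles. In the coaching sections and the cost analysis it belongs to what is being tested; in the outcome section it is measuring equipment sent to anyone who lacks it. The move to telephone enrolment put the second role ahead of randomisation, and the definition of the control arm was not updated.

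What is at stake is the claim. A report that follows the plan as written would describe the effect as coaching against usual care plus a pamphlet, although some controls also held a study-supplied monitor for the year. The SAP also asks whether treatment effects differ after COVID. A smaller remote-phase effect could be read as telephone coaching working less well, when the comparator had also changed.

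**Working it through.** **1. Who has a study-supplied monitor, and when** (supply rule, telephone enrolment and order of randomisation taken together)

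| Participant | Mailed before randomisation? | Monitor in follow-up | Stated comparator correct? |
|---|---|---|---|
| Phone-enrolled control, owned none | Yes | Yes, as no return is mentioned | No |
| Phone-enrolled intervention, owned none | Yes | Yes | Not applicable |
| Phone-enrolled, owned one, either arm | No | Yes, their own | Yes as to the monitor |
| In-person control, owned none | No; mailed only around the exit call | Largely no | Yes |

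The scale follows the same pattern: it is an intervention-bag item in Protocol 5.2, but is mailed in either arm under 5.5.

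**2. What still separates the arms.** The coaching calls, goal setting, a pressure reading at each coach call, and feedback to the participant and provider remain confined to the intervention arm. Only access to the device stops being a difference.

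**3. Can the effect be sized?** The plan's own sample size comes first. Inputs (Protocol 5.6): 5 mmHg, SD 14.2, two-sided 0.05, 80% power, provider ICC 0.015 with clusters of 5, coach ICC 0.007 with clusters of 35, 15% attrition.

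- Unclustered: 2 × (14.2 × (1.96 + 0.84)/5)² ≈ 127 per arm.
- Design effects: control 1 + 4 × 0.015 = 1.06; intervention 1.06 + 34 × 0.007 = 1.298; mean 1.179.
- This gives 150 per arm, 300 in total, and 300/0.85 = 353 against the stated 354. The figure reproduces.
- At 170 per arm (200 × 0.85), SE = 14.2 × √((1.06 + 1.298)/170) ≈ 1.67 and power at 5 mmHg is 84.8%. At the protocol's 177 per arm it is 86.2%.

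Any reduction of the whole-trial contrast would be f × b. Here f is the share of controls who enrolled by phone and owned no monitor, and b is the mean fall in systolic pressure from a monitor without coaching. **The documents give neither.** Purely as assumptions, at 170 per arm:

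| f | b (mmHg) | 5 − f × b | Power |
|---|---|---|---|
| any | 0 | 5.0 | 84.8% |
| 0.1 | 2 | 4.8 | 81.9% |
| 0.3 | 2 | 4.4 | 74.9% |
| 0.5 | 4 | 3.0 | 43.4% |

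The answer runs from no loss to a large one, depending only on what is assumed. Starting from 5 mmHg is itself an assumption: the protocol takes that figure from other peer-support and community health worker studies and does not say that it includes a monitor effect.

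**4. The COVID analyses (SAP section 6).** The sensitivity analysis selects on enrolment after the pandemic, which tracks the change of comparator. The exploratory comparison splits on when the 12-month outcome was collected. Its later group can therefore mix in-person enrolees, whose comparator was unaltered, with phone enrolees. In both analyses the comparator changes along with delivery mode.

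**5. Would an arm-by-ownership interaction repair it?** No. After mailing, neither ownership stratum contains phone-enrolled controls without a monitor. It would also be imprecise. Assume that 25–50% of 340 evaluable participants (85–170) are remote and 25–50% of those owned no monitor. Ignoring clustering, SE = 2 × 14.2 × √(1/m₁ + 1/m₂). This is 4.4 mmHg for strata of 85 and 85, and 7.1 for 21.25 and 63.75. The interaction detectable with 80% power is about 2.8 SE, or 12–20 mmHg.

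**The case against.** The best defence has four parts.

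- **A mailed device is not the intervention component.** In coaching, the cuff comes with recorded readings, a measurement at each call and feedback to the provider. Controls get a device for two measurement sessions. This stands as a reason not to presume an effect of possession. It does not rescue the comparator's description, because the plan itself offers cuffs for home monitoring, cites evidence for that, and lists monitors as intervention material.
- **Supply is arm-neutral and precedes randomisation.** This stands in full. It makes remote measurement possible in both arms and introduces no difference between them.
- **Post-COVID analyses are already planned.** True, but neither document says that the comparator changed, and those analyses also carry the switch from home visits to telephone. They cannot isolate the monitor.
- **Costs are limited to materials used in the intervention.** This largely stands. Aim 3 also excludes trial-specific costs, although it says so for staff activities. What remains is an ambiguity about monitors mailed for measurement.

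A reader might infer more: that the effect is diluted, that power is lost, or that the comparison is biased. The documents support none of these. Dilution is the plausible direction, but it needs three quantities that are absent: the remote share, the ownership rate and the effect of a monitor without coaching. Bias does not follow, because the monitor was supplied without regard to arm.

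**Conclusion.** The stated comparator is wrong for controls enrolled by phone who owned no monitor, and in the same way for those who lacked a scale. For the remote phase the trial estimates coaching with a monitor available in both arms. It does not estimate coaching plus monitor against usual care plus a pamphlet. The contrast may be smaller as a result, but no size or loss of power can be claimed. The randomised comparison is valid for the comparator as delivered, and controls enrolled in person are largely unaffected.

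This rests on the supply rule being applied as written, on devices not being recalled, and on some controls having enrolled by phone without a monitor. The SAP expects enrolment during the remote period but gives no count.

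**What to change.** 1. **Comparator and claim.** In Protocol 5.1 c) and SAP section 6, state the remote-phase comparator as usual care plus education plus a study-supplied monitor or scale where none was owned. Reconcile SAP section 5 with Protocol 5.5 on who measures pressure and with what device. Word the trial conclusion and the pre/post-COVID interpretation to match. Say that the comparator changed along with delivery mode, and that this change follows enrolment mode rather than the date of the exit measurement.
2. **Reporting.** Give, by arm, how many already owned and how many were mailed a device. Staff already ask at scheduling; if the answer was not kept, mailing records may supply it. Show the arm effect among prior owners as a descriptive supplement, with its interval, and not as an interaction test.
3. **Cost.** In the Aim 3 analysis, show monitors mailed for outcome measurement separately from those offered in coaching. Simply deleting the former could understate the cost of a programme that offers cuffs.

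The price is a slightly narrower claim, one recorded field, one descriptive estimate and one cost line. Conduct and sample size do not change. If ownership cannot be recovered, the wording correction still applies.
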